Other secondary endpoints on quality of life defined as the change from baseline will be analyzed by means of paired (samples) t-test or Wilcoxon signed rank sum test according to the normal or non-normal distribution. The mean change will be displayed together with their 95% confidence interval (95%CI).

The secondary endpoint on HbA1c change over time (baseline, 6- and 12-months follow-up) will be analyzed by means of mixed models for repeated measures. The dependent variable will be pre-log transformed depending on normal or non-normal distribution. The model will have the clinical outcomes as dependent variables and baseline values and visits as explanatory variables. All assumptions for regression models will be performed by assessment of plots of the residual values. Difference between visits means will be tested by applying contrast on the estimated model. The plot for the mean change over time will be reported.

It is anticipated that SAS (SAS Institute Inc., Cary, NC, USA) will be used to perform all statistical analyses. Statistical tests will be based on a one-sided significance level of 0.05, and possible interaction effects will be evaluated at a significance level of 0.10. No adjustments for multiple comparisons will be performed. Additional exploratory analyses will be conducted as deemed appropriate.

Procedures for reporting any deviation(s) from the original statistical plan including that justification will be documented.

13. Ethics

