7.1.3. Analysis Sets

The following subject sets will be used for the analysis:

- The Intention To Treat (ITT) includes all patients enrolled in the study with signed Data Release Form, fulfill the inclusion and exclusion criteria. The ITT will be used for all endpoints and safety evaluation.
- The Per Protocol (PP) includes all patients enrolled in the study with signed Data Release Form, fulfill the inclusion and exclusion criteria and having at least 70% of time using the Auto Mode during the 6-month follow up. The PP set will be used for all endpoints.

The primary analysis will be performed on the ITT set. As sensitivity analysis the PP set will be used. The following table shows how each population set will be used for analyses:

Population set	Baseline assessment	Primary Endpoint	Secondary Endpoints	Adverse Events
PP	✓	✓*	✓	
ITT	✓	✓	✓	✓

* The primary endpoint on the PP population will be considered as sensitivity analysis

For patients who dropout, the analyses will include all data up to the point of their last data collection.

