7.4. Handling of Missing, Unused, and Spurious Data and Dropouts

Since the impact of missing data is expected to be small, no imputation of missing data will be performed.

In the case of dates collected at baseline with missing day and/or month the next procedure will be applied. A missing day and month will be imputed using the month 'July 1' and a missing day will be imputed with the day '15'. This applies only to dates related to medical history and baseline information with missing month and/or day.

For per protocol analysis, if HbA1c is collected out of window (-30 days from the date of actual Baseline visit and \pm 30 days from the date of actual Follow-up visit), HbA1c will be considered missing for that period/visit.

Outliers and influential observations will be identified via graphical plots. Once outliers or influential observations are identified, the study team will be informed and according to their decision the analysis for primary endpoint may be repeated using a statistical method robust against outliers. Additional exploratory analyses will be conducted as deemed appropriate.

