7.9.7. Glycemic parameters

The objective is to evaluate the change in glycemic parameters at baseline and every three months until 12 months. The time of sensor glucose values below 70mg/dL and below 54mg/dL and the time of sensor glucose value above 180mg/dL and above 250mg/dL will be analyzed by means of GEE (generalized estimating equation) models or random effects models with random intercept as appropriate, for continuous outcomes to account for repeated measures using patient ID as the subject. The dependent variable will be pre-log transformed depending on normal or non-normal distribution. The model will have the glycemic parameter as dependent variable and baseline values and visits as explanatory variables. All assumptions for regression models will be assessed by viewing plots of the residual values. The plot for the mean change over time will be reported for the glycemic parameters and for graphical purpose only separately by population as deemed appropriate.

The HbA1c will be analyzed at 6 months and at 12 months by means of paired (samples) t-test or Wilcoxon signed rank sum test according to the normal or non-normal distribution. In addition, the mean change from baseline to 6 and 12 months, respectively, will be displayed together with their 95% confidence interval (95%CI).

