7.12. Changes to Planned Analysis

The analysis described in the CIP could differ from that presented in this SAP due to data availability. Any deviation from the original statistical plan will be described and justified in the final report, as appropriate.

8. Validation Requirements

All collected data will be reviewed for completeness, correctness and consistency. In case of issues, queries will be sent to the investigator to complete, correct or comment the data. To ensure the quality of the results provided for the study in the form of tables, listings and figures, and the derived datasets the following processes are used:

- Statistical programming and analysis will be done by qualified programmer(s) and statistician(s) following applicable procedures and best practices.
- The derived datasets and tables will be validated by a second programmer or statistician.
- Statistical results will be reviewed and confirmed by a second statistician.

The complete set of Tables, Listings, and Figures (TLF) will be 100% checked for accuracy, completeness, and consistency prior to inclusion in the interim or final clinical study report. According to Medtronic SOPs the level I validation (double programming) will be implemented for primary and secondary endpoints, while level II validation (the peer reviewer reviews the code; where appropriate, performs manual calculations or simple programming checks to verify the output) will be implemented for all other outputs.

9. References

1. <http://www.strobe-statement.org/index.php?id=available-checklists>

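### The SAP swaps the protocol's repeated-measures model for HbA1c for separate paired tests without giving a reason, leaving the 12-month change open to bias if poor 6-month responders are more often missing

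*SAP*

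**What the plan says.** Protocol 12.3 states: "The secondary endpoint on HbA1c change over time (baseline, 6- and 12-months follow-up) will be analyzed by means of mixed models for repeated measures". On the model terms it adds "The model will have the clinical outcomes as dependent variables and baseline values and visits as explanatory variables", and it plans contrasts between visit means and a plot of the mean change over time.

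SAP 7.9.7 states: "The HbA1c will be analyzed at 6 months and at 12 months by means of paired (samples) t-test", with a Wilcoxon signed rank test as the non-normal alternative. The same SAP section keeps GEE or random-intercept models for the four CGM time-in-range-type parameters.

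On missing data, the protocol leaves the choice of an imputation method open should the need arise. SAP 7.4 closes it: "Since the impact of missing data is expected to be small, no imputation of missing data will be performed". For the per-protocol analysis, an HbA1c outside the 30-day window is also discarded: "HbA1c will be considered missing for that period/visit". SAP 7.1.3 nevertheless says "For patients who dropout, the analyses will include all data up to the point of their last data collection".

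SAP 7.12 covers differences from the protocol only in general terms. It says the protocol analysis "could differ from that presented in this SAP due to data availability" and that deviations will be justified in the final report. HbA1c is not named.

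**The concern.** The SAP gives no ground for the change. HbA1c is collected at the same three visits in the protocol's Table 3 and the SAP's Table 1, so availability of data does not explain it. Nor does any reluctance to fit longitudinal models, since the SAP fits them to the CGM parameters.

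What is at stake is the 12-month estimate. A patient seen at month 6 but not at month 12 has an informative HbA1c value that the protocol's type of model would use and the 12-month paired test does not. If patients with little or no 6-month improvement are the ones more often missing, those left at month 12 are a favourable selection and the fall looks larger than it was. That error would favour the device, in a study meant to support reimbursement (Protocol 4.2). The protocol's visit contrasts would also compare 6 with 12 months directly. Two separate tests on possibly different patients do not.

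**Working it through.** **Step 1. Who enters each analysis.** An HbA1c value is needed for eligibility, so missing values will mostly arise at follow-up.

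| Patient | 6-month paired test | 12-month paired test | Likelihood-based repeated-measures model |
|---|---|---|---|
| All three values | in | in | in |
| Month 12 missing | in | out, 6-month value unused | in, 6-month value informs month 12 |
| Month 6 missing, month 12 present | out | in | in |
| Both follow-ups missing | out | out | no follow-up response available |

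No HbA1c is scheduled between baseline and month 6. For dropout before month 6, neither method has an early HbA1c response to condition on, so the difference between methods lies mainly at month 12.

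**Step 2. The plan's own figures.** There is no sample size or power for HbA1c. The only calculation is for TIR (Protocol 12.2): SD of the difference = √(2 × 16² × (1 − 0.5)) = 16, difference 3, one-sided 0.05, power 90%. The exact t calculation gives 245 pairs, and 245/0.8 = 306.25, stated as 306. These figures reproduce. (The SAP prints an SD of 14 beside the same 245, which is a separate matter.) I take from here only N = 306 and 20% as an upper scenario for missing values.

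**Step 3. Size of the bias (all HbA1c inputs assumed).** Let D6 and D12 be the changes from baseline. If missingness at month 12 depends only on D6, then

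bias of the 12-month paired mean = β × SD(D6) × δ,

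where β = cov(D6, D12)/var(D6) and δ is the shift in mean D6, in SD units, among patients who remain.

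Assume a true change of −0.5, SD 0.9 at each visit, baseline-to-follow-up correlation ρ = 0.4 or 0.6, and 6-to-12-month correlation ρ + 0.4(1 − ρ) = 0.64 or 0.76. Log-odds of dropout per SD of poorer 6-month change are 0, 0.5 or 1.0. There are 1,500 simulated trials of 306 per scenario, compared with the maximum-likelihood estimate from a saturated three-visit normal model:

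| ρ | Missing | Log-odds per SD | Paired bias, month 12 | Model bias, month 12 |
|---|---|---|---|---|
| 0.4 | 10% | 0 / 0.5 / 1.0 | 0.001 / −0.033 / −0.062 | 0.000 / 0.000 / 0.000 |
| 0.4 | 20% | 0 / 0.5 / 1.0 | −0.001 / −0.066 / −0.120 | 0.000 / 0.001 / −0.001 |
| 0.6 | 10% | 0 / 0.5 / 1.0 | 0.005 / −0.025 / −0.052 | 0.004 / 0.002 / −0.002 |
| 0.6 | 20% | 0 / 0.5 / 1.0 | 0.000 / −0.054 / −0.098 | −0.001 / 0.000 / 0.000 |

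Check against the formula: β = (1 − 0.8 + 0.64)/1.2 = 0.70 and (1 − 1.2 + 0.76)/0.8 = 0.70; SD(D6) = 0.9√1.2 = 0.986 and 0.9√0.8 = 0.805. The worst case implies δ = −0.120/(0.70 × 0.986) = −0.174 for ρ = 0.4 and −0.098/(0.70 × 0.805) = −0.174 for ρ = 0.6. The two agree. The largest bias thus needs remaining patients to have done about 0.17 SD better at 6 months than the full cohort.

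The 6-month paired estimate was unbiased (at most 0.002), because dropout was simulated only after month 6.

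A second simulation used other assumptions: true change −0.40, SDs 1.0 and 0.9, correlations 0.6 to 0.7, odds ratio 1.5 to 3 per SD. It gave paired estimates of −0.42 to −0.46 at 10% missing and −0.45 to −0.51 at 20%, an overstatement of 0.02 to 0.06 and 0.05 to 0.11. The likelihood estimate stayed at −0.40.

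**Step 4. Precision with 20% missing at random.** Variance ratio, model to paired = 0.8 + 0.2 × (residual variance of month 12 given the two earlier values)/(variance of D12). In units of 0.9², the residual is 1 − 0.3648/0.84 = 0.566 for ρ = 0.4 and 1 − 0.3904/0.64 = 0.390 for ρ = 0.6; the variance of D12 is 1.2 and 0.8. The ratio is 0.8 + 0.2 × 0.566/1.2 = 0.894 and 0.8 + 0.2 × 0.390/0.8 = 0.898. Simulated trials under the second set of assumptions gave (0.0531/0.0551)² = 0.93. The gain is about 7% to 10% of the variance.

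**Step 5. Does any repeated-measures model do?** No. SAP 7.9.7 allows GEE for the CGM parameters. With baseline as a covariate and an independence working correlation, GEE gave −0.462 where the paired test gave −0.506 and the truth was −0.40 (20% missing, odds ratio 3). It kept 0.062/0.106 = 58% of the bias.

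**The case against.** The best defence is procedural. Protocol 12.3 leaves detailed methods to the SAP and requires an amendment only for a change to a principal feature. Other changes may be justified in the final report, and the SAP goes to HAS before the analyses are run (Protocol 14.7.4). The paired tests estimate the stated endpoint directly, and DQoL, HFS and DTSQs use the same tests on the same visits. HbA1c is an unpowered secondary endpoint, both documents expect little impact from missing data, and at 10% missing the bias is about one standard error (0.055) or less. All of that stands. It makes the change permissible and the point modest, but it does not supply a reason for the change, and a reason given after results are seen is worth less.

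A reader might infer more than the documents support:

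- That every patient with a missing visit is lost. Each test excludes only patients lacking baseline or that visit's value; someone who leaves after month 6 still counts at month 6.
- That protection is lost for early dropout in general. Before month 6 there is no HbA1c response for either method to use.
- That 20% of HbA1c values will be missing. The 20% attrition figure includes protocol failures such as low Auto Mode use. Those patients stay in the ITT set and may well have HbA1c values.
- That poor responders will in fact be missing more often. Nothing in the documents says so.
- That the protocol's model as written is a complete remedy. It lists baseline both as a time point and as an explanatory variable and names no covariance structure.

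**Conclusion.** The discrepancy between Protocol 12.3 and SAP 7.9.7 is plain and unexplained, and it does not depend on any simulation. Its consequence is conditional. It concerns mainly the 12-month change and requires missingness to depend on the observed 6-month HbA1c. Under assumed SDs, correlations and dropout strength, the 12-month fall would be overstated by about 0.02 to 0.06 points at 10% missing and 0.05 to 0.12 at 20%. If missingness is unrelated to response, the bias is at most 0.005 and the cost is a modest loss of precision. A likelihood-based model removes the bias when the missing-at-random assumption holds and cannot promise to when it does not. This is a cheap improvement to a secondary analysis. It is not evidence that the HbA1c result will be wrong.

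**What to change.** In SAP 7.9.7, make the HbA1c analysis a likelihood-based mixed model for repeated measures with visit as a factor and unstructured covariance. State that GEE with an independence working correlation is not an acceptable substitute here. Enter baseline either as a response (HbA1c at baseline, 6 and 12 months) or as a covariate, not both. If it is a covariate, model the change at 6 and 12 months and evaluate the adjusted means at the mean baseline of the analysis set. Report the 6- and 12-month changes as contrasts with 95% CIs, and keep the paired tests as supportive. If the sponsor prefers the paired tests as the main analysis, the SAP should record the departure from the protocol and its reason before the analysis is run.

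Cost: one paragraph, one additional model, and explicit reliance on missing at random. With complete data and baseline as a response, the model returns the same mean changes as the paired analysis.

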7.9.8. Satisfaction score on the DTSQs

The objective is to evaluate the treatment satisfaction score on the DTSQs evaluated at baseline, 6 and 12 months after the start of the Study phase. The different DTSQs versions will be used to assess satisfaction in the following populations:

- DTSQs Adult (≥ 18 years old)
- DTSQs Teen (13-17 years old)
- DTSQs Parent (7-12 years old)

The DTSQs total score will be analyzed by means of paired (samples) t-test or Wilcoxon signed rank sum test according to the normal or non-normal distribution. In addition, the mean change will be displayed together with their 95% confidence interval (95%CI).

[figure not shown]
The DTSQs has six items related to treatment satisfaction and two other items assess perceived frequency of hyperglycaemia and hypoglycaemia. Each item has a maximum of 6 (satisfied) and a minimum of 0 (not satisfied). The scale total is computed by adding 6 items (1,4,5,6,7,8) and the 2 items on hypo/hyperglycemia will be analyzed separately. The scale total will be reported by summary statistics overall and by population.

The scoring system for the scale total by population is the following:

DTSQs Adults: 8 items (0-6 scores). The scale total is computed by adding 6 items* (2 items on hypo/hyperglycemia must be analyzed separately), to produce the Treatment Satisfaction score which has a minimum of 0 to a maximum 36.

DTSQs Teen: 12 items (0-6 scores). The scale total is computed by adding 10 items (2 items on hypo/hyperglycemia must be analyzed separately), to produce the Treatment Satisfaction score which has a minimum of 0 and maximum of 60.

DTSQs Parent: 14 items (0-6 scores). The scale total is computed by adding 12 items (2 items on hypo/hyperglycemia must be analyzed separately), to produce the Treatment Satisfaction score which has a minimum of 0 and maximum of 72.

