7.9. Evaluation of Objectives

In this section a detailed information about each objective is included together with calculations and derivations of outcome parameters, analysis methods, datasets analyzed (PP and ITT). For each endpoint will be reported at least summary statistics table. All the objectives will consider two study phases calculated as defined in section 7.7. The secondary endpoints on questionnaires will include three subpopulations according to the age at the Consent date: Adult (≥ 18 years old), Teen (13-17 years old) and Parent (7-12 years old). This subpopulation definition will be maintained over the study visits.

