7.9.4. Satisfaction score based on the DTSQc

To evaluate the satisfaction score based on the DTSQc evaluated at 6 months. The different DTSQc versions will be used to assess satisfaction in the following populations:

- DTSQc Adult (≥ 18 years old)
- DTSQc Teen (13-17 years old)
- DTSQc Parent (7-12 years old)

[figure not shown]
The DTSQc has six items related to treatment satisfaction and two other items assess perceived frequency of hyperglycaemia and hypoglycaemia. Each item has a maximum of 3 (more satisfied now) and a minimum of -3 (less satisfied now) with a midpoint of 0 reflecting no change. The scale total is computed by adding all items excluding two items (2,3) on hypo/hyperglycemia which will be analyzed separately. The scale total will be reported using summary statistics for each population. All values greater than 0 will be defined as an improvement. Although this endpoint was not powered for testing, the DTSQc will be also analyzed by means of one sample Z-score test or Wilcoxon signed rank sum test according to the normal or non-normal distribution.

The scoring system for the scale total by population is the following:

DTSQc Adults: 8 items (-3/3 scores). The scale total is computed by adding 6 items (excluding two items (2,3) on hypo/hyperglycemia that must be analyzed separately), to produce the Treatment Satisfaction score which has a minimum of -18 and 18.

DTSQc Teen: 12 items (-3/3 scores). The total score is computed by adding the 10 items (2 items on hypo/hyperglycemia must be analyzed separately) to produce the Treatment Satisfaction score, which has a minimum of -30 and 30.

DTSQc Parent: 14 items (-3/3 scores). The total score is computed by adding the 12 items (2 items on hypo/hyperglycemia must be analyzed separately) to produce the Treatment Satisfaction score, which has a minimum of -36 and 36.

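### SAP 7.9.8 asks for an overall DTSQs total, but the three version totals have different ranges (0–36, 0–60, 0–72) and no common scaling is given

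*SAP*

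**What the plan says.** On reporting, SAP 7.9.8 states: "The scale total will be reported by summary statistics overall and by population". Each item is scored 0 to 6, and the section gives one scoring rule per version:

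- Adult: 6 of 8 items are summed, giving a "Treatment Satisfaction score which has a minimum of 0 to a maximum 36".
- Teen: "DTSQs Teen: 12 items (0-6 scores). The scale total is computed by adding 10 items", with a maximum of 60.
- Parent: 12 of 14 items are summed, giving a "Treatment Satisfaction score which has a minimum of 0 and maximum of 72".

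No mean item score, percentage of maximum or other rescaling appears in either document. SAP 7.2 lists the statistics to be shown for any continuous variable, including the mean, SD, median and maximum.

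Just before the reporting instruction, 7.9.8 has a general sentence that names no version: "The scale total is computed by adding 6 items (1,4,5,6,7,8"). For the test, 7.9.8 specifies a paired t or signed-rank test and does not say whether it is run by version. SAP 7.9 adds that "The secondary endpoints on questionnaires will include three subpopulations according to the age at the Consent date", and that a subject's group is then kept at all visits.

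The sister section on the DTSQc (SAP 7.9.4) has no overall row: "The scale total will be reported using summary statistics for each population". Its general summation rule is "The scale total is computed by adding all items excluding two items (2,3) on hypo/hyperglycemia".

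**The concern.** A raw sum of 12 items is larger than a raw sum of 6 items at the same level of satisfaction. Pooling the three raw totals in one row gives a figure with no fixed range, whose location and spread move with the shares of adults, teens and parents.

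DTSQs satisfaction is the protocol's secondary objective #6, in a study intended to support reimbursement in France. The protocol's rationale (section 6.1) describes the satisfaction score as running from 0 to 36. Someone comparing the overall row with that range, or with another cohort of different age mix, would be misled. At stake is whether this row can be interpreted, not the by-version results.

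**Working it through.** **Inputs from SAP 7.9.8.** Items are scored 0–6. Items summed: 6 (adult), 10 (teen), 12 (parent).

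**Step 1: reproduce the stated maxima.** Maximum = items summed × 6. This gives 6 × 6 = 36, 10 × 6 = 60 and 12 × 6 = 72, all as stated. The ranges are real differences in scale length, not misprints.

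**Step 2: hold satisfaction equal.** Assume a mean of 4.0 per item in every version (an assumption for illustration). Raw totals are 6 × 4 = 24, 10 × 4 = 40 and 12 × 4 = 48. As a share of maximum they agree: 24/36 = 40/60 = 48/72 = 66.7%.

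**Step 3: form the overall row.** The documents give no age mix, so adult/teen/parent shares are assumed. With shares a, t, p:

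overall mean = 24a + 40t + 48p

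between-version SD = √[a(24 − mean)² + t(40 − mean)² + p(48 − mean)²]

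| Assumed mix | Raw overall mean | SD from scale length alone | % of maximum |
|---|---|---|---|
| 100/0/0 | 24.0 | 0 | 66.7 |
| 80/10/10 | 19.2 + 4.0 + 4.8 = 28.0 | √(12.8 + 14.4 + 40.0) = 8.2 | 66.7 |
| 60/20/20 | 14.4 + 8.0 + 9.6 = 32.0 | √(38.4 + 12.8 + 51.2) = 10.1 | 66.7 |
| 30/35/35 | 7.2 + 14.0 + 16.8 = 38.0 | √(58.8 + 1.4 + 35.0) = 9.8 | 66.7 |

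The mean moves by 14.0 points across these mixes with no difference in satisfaction. The SD is inflated by variation that belongs to the questionnaires and not to the subjects.

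**Step 4: vary the assumed item score.** With equal teen and parent shares at 4.0 per item, mean = 24a + 44(1 − a) = 44 − 20a, so each 10-percentage-point lower adult share adds 2.0 points. At 3.0 per item it adds 1.5, and at 5.0 per item 2.5. The direction does not depend on the item score chosen.

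**Step 5: compare with the 0–36 range in the protocol.** The mean number of items summed is 7.0, 8.0 and 9.5 in the three mixed cases. The raw overall mean exceeds 36 once the mean item score passes 36/7.0 = 5.14, 36/8.0 = 4.50 or 36/9.5 = 3.79. Only the last mix crosses that line at 4.0 per item.

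**The case against.** **By-version results stand beside the overall row.** The same sentence that orders the overall figure also orders it by population, with numbers of subjects. A reader can see the mix and the version-specific totals. Each subject keeps one version, so within this single-arm study the mix shifts between visits only through dropout or missing forms. This stands. It limits the harm to the overall row but does not make that row meaningful.

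**The six-item sentence.** A reader might infer that it contradicts the teen and parent rules and leaves the total undefined, or that the overall row means a common six-item score. The documents do not support either. The sentence matches the adult rule and the protocol's generic description of the DTSQ, and explicit rules for each version follow it. It reads as adult wording without a label, which the specific rules override. A common six-item total is never stated, and items 1, 4, 5, 6, 7 and 8 are not mapped to the longer versions. The adult rule carries an asterisk with no visible note. A note may have been lost in the text, so nothing is made of it.

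**A pooled test.** A reader might also infer that the paired test pools the raw totals, so that teens and parents dominate the result. The SAP does not say so. Its three questionnaire subpopulations make testing by version the natural reading, although 7.9.8 should state it.

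**The DTSQc section as a model.** SAP 7.9.4 is a sound precedent for summarising by version, and its summation rule fits all three lengths. It is not free of the labelling problem. It too describes the questionnaire as having six satisfaction items without naming the adult version, and it does not map items 2 and 3 to the teen and parent forms.

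**Conclusion.** The point holds for one output. As written, SAP 7.9.8 orders an overall DTSQs summary of raw totals with maxima of 36, 60 and 72, and neither document supplies a common scale. At identical satisfaction of 4.0 per item, the overall mean can be 24.0, 28.0, 32.0 or 38.0 depending only on the age mix. The mismatch of ranges is certain from the text. The size rests on assumed age shares and an assumed equal item score, because the documents give neither.

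It does not follow that secondary objective #6 as a whole is compromised. By-version summaries and within-person changes remain valid, and the primary endpoint and sample size are not touched. The six-item sentence is a labelling matter only.

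**What to change.** **Preferred.** Remove the overall summary from SAP 7.9.8 and state that the DTSQs total is summarised and tested separately for the adult, teen and parent versions. This follows the by-population DTSQc summaries in 7.9.4 and makes the level of the test explicit.

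**Alternative.** If an overall figure is wanted, base it on the mean item score or on the percentage of the version's maximum. State beside it that it still combines different item sets, and parent reports with self-reports.

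**In either case.** Limit the general six-item sentence in 7.9.8 to the adult version. The unlabelled six-item description of the DTSQc in 7.9.4 can be labelled at the same time.

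**Cost.** Two sentences change in 7.9.8, plus one derived variable if the rescaled figure is chosen. No new data are needed, and no by-version result changes.
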